2.5 STUDY SAMPLE SIZE DETERMINATION

A total of 150 participants is considered sufficient to obtain initial safety data for VLA2001, especially since inactivated vaccines are a well-established, safe vaccine technology. Fifty participants per group will allow for 95% confidence that an AE with a true underlying incidence of about 2% would be observed in the present study.

In addition, assuming 10% of participants with protocol deviations, about 45 participants per dose group will be evaluable for immunogenicity. This sample size is in a range generally expected to allow selection of an appropriate dose level.

For the Booster Phase of this study, no formal sample size calculation has been performed and no minimal or maximal number of participants is defined. Based on operational considerations the total number of participants is expected to be up to approximately 80.

2.6 TREATMENT ASSIGNMENT AND BLINDING

For the blinded part, IMP will be provided to the study sites in a blinded manner, i.e. no visual differentiation will be possible, same volumes will have to be administered for all dose groups. Identification of and allocation of the syringe to a specific participant is ensured by placing a tear-off label containing a kit number, Participant number, date of injection and operator onto the label.

For the booster phase, VLA2001 vaccine will be administered as open label.

2.7 ADMINISTRATION OF TRIAL MEDICATION

The vaccination schedule consists of two doses of VLA2001 for each study participant, administered by intramuscular (IM) injection in the deltoid region of non-dominant arm preferably 21 days apart, on Day 1 and Day 22 [Low dose, Medium dose, High dose].

The booster vaccination will be administered IM in the deltoid region of the non-dominant arm.

For primary immunization, one part of the vaccine (labelled VLA2001) will be presented as a liquid formulation containing aluminium hydroxide in glass vials at three dose levels (each vial is pre-filled with 0.4ml) and has to be mixed bedside with CpG 1018 (0,2ml) prior to vaccination (volume for administration is 0.5ml).

For the Booster Phase, there will be no bed-side mixing necessary. VLA2001 will be provided in multi-dose vials to the study sites where each multi-dose vial will have a unique kit number.

2.8 SCHEDULE OF ASSESSMENTS AND PROCEDURES

For the schedule of study procedures and assessments refer to protocol section 22.2 and 22.3.

3 ENDPOINTS

3.1 SAFETY ENDPOINTS

3.1.1 Primary Endpoint

Frequency and severity of solicited adverse events (AEs) (local and systemic reactions) within 7 days after any vaccination of the primary vaccination series.

3.1.2 Secondary Endpoints

- Frequency and severity of any unsolicited AE until Day 36.
- Frequency and severity of any vaccine-related AE until Day 36.
- Frequency and severity of any AE until Day 208.
- Frequency and severity of any vaccine-related AE until Day 208.
- Frequency and severity of any SAE until Day 36.
- Frequency and severity of any AESI until Day 36.
- Frequency and severity of any SAE until Day 208.
- Frequency and severity of an AESI until Day 208.

Booster Phase:

- Frequency and severity of solicited AEs (local and systemic reactions) within 7 days after the booster vaccination
- Frequency and severity of any unsolicited AE up to Visit 9
- Frequency and severity of any vaccine-related AE up to Visit 9
- Frequency and severity of any SAE up to Visit 10
- Frequency and severity of any AESI up to Visit 10

3.2 IMMUNOGENICITY ENDPOINTS

3.2.1 Primary Endpoint

Geometric mean titre (GMT) for neutralizing antibodies against SARS-CoV-2 determined by wild-type virus microneutralizing assay at Day 36.

3.2.2 Secondary Endpoints

- Immune response as measured by neutralizing antibody titres against SARS-CoV-2 on Day 8, Day 22, Day 106 and Day 208.
- Proportion of participants with seroconversion in terms of neutralizing antibodies on Day 8, Day 22, Day 36, Day 106 and Day 208.
- Fold increase of SARS-CoV-2 neutralizing antibody titres on Day 8, Day 22, Day 36, Day 106 and Day 208 compared with baseline.
- GMTs for IgG against SARS-CoV-2, determined by ELISA, at Day 1, 8, 22, 36, 106 and 208.
- Proportion of participants with seroconversion in terms of IgG antibodies against SARS-CoV-2 as determined by ELISA on Day 8, Day 22, Day 36, Day 106 and Day 208.

Booster Phase:

- Geometric mean fold rise (GMFR) from pre-booster time point (Visit 7) to 2 weeks after booster dose (Visit 8) with regards to neutralizing antibodies.
- Geometric mean fold rise (GMFR) from pre-booster time point (Visit 7) to 4 weeks after booster dose (Visit 9) with regards to neutralizing antibodies.
- Proportion of Participants with 4-fold increase from pre-booster dose (Visit 7) to 2 weeks after booster dose (Visit 8) with regards to neutralizing antibodies.
- Proportion of Participants with 4-fold increase from pre-booster dose (Visit 7) to 4 weeks after booster dose (Visit 9) with regards to neutralizing antibodies.
- Geometric mean titres (GMT) measured as neutralizing antibody titres against SARSCoV-2 at Visit 7, Visit 8 and Visit 9.
- Geometric mean fold rise (GMFR) from pre-booster dose (Visit 7) to 4 weeks after booster dose (Visit 9) with regards to S-protein binding antibodies (ELISA).
- Geometric mean fold rise (GMFR) from pre-booster dose (Visit 7) to 2 weeks after booster dose (Visit 8) with regards to S-protein binding antibodies (ELISA).
- Proportion of Participants with 4-fold increase from pre-booster dose (Visit 7) to 4 weeks after booster dose (Visit 9) in regards to S-protein binding antibodies (measured by ELISA).

- Proportion of Participants with 4-fold increase from pre-booster dose (Visit 7) to 2 weeks after booster dose (Visit 8) in regards to S-protein binding antibodies (measured by ELISA).
- GMT measured as IgG antibodies against SARS-CoV-2, as determined by ELISA, at Visit 7, Visit 8 and Visit 9.

3.3 EXPLORATORY ENDPOINT

Cellular immune response on Day 1, Day 36, Day 208, Visit 7 and Visit 8.

4 ANALYSIS POPULATIONS

4.1 SAFETY ANALYSIS SET (SAS)

The Safety Analysis Set (SAS) includes all participants who entered into the study and received at least one vaccination. The SAS will be used for all baseline, safety and tolerability analyses including demographic data, local/systemic tolerability, laboratory data, Adverse Events (AEs), Serious Adverse Events (SAEs) and Adverse Events of Special Interest (AESIs). All analyses based on the SAS will be carried out using the actual treatment received.

4.2 FULL ANALYSIS SET (FAS)

The Full Analysis Set (FAS) is defined to include all participants enrolled who received at least one vaccination. Participants will be analysed according to the treatment group they had been randomized to i.e. the planned treatment, rather than by the actual treatment they received.

4.3 PER-PROTOCOL ANALYSIS SET (PPAS)

The Per-Protocol Analysis Set (PPAS) will consist of the FAS population including participants who have no major protocol deviations until the respective analysis time point (i.e. PPAS Day 36, PPAS Day 106 and PPAS Day 208). Participants who received an already licensed COVID-19 vaccine outside of the study or participants who received less than 2 vaccinations will be excluded.

These criteria for potential protocol violations are identified at the time of study planning. However, during the course of the trial unforeseen events may occur or new scientific knowledge may become available, therefore final decisions on all protocol violations will be made on a case by case decision in a data review meeting.

Immunogenicity analysis will be primarily carried out on the PPAS.

4.4 MODIFIED PER-PROTOCOL ANALYSIS SET (mPPAS)

Modified PPAS will include all participants from PPAS except those participants who were tested positive for COVID-19 anytime during study until the respective analysis timepoint (i.e. PPAS Day 36, PPAS Day 106 and PPAS Day 208) after first vaccination.

4.5 PROTOCOL DEVIATIONS

Any deviations from the protocol will be tracked, actions defined, as feasible, and reviewed in data review meetings for assessment of their influence on the quality of the study analysis.

All deviations will be evaluated and classified as major or minor before database lock and unblinding (refer to protocol deviation management plan for more details). All deviations will be listed.

Major protocol deviations that lead to exclusion from the PP Population may include the following but are not limited to:

- Participants with less than two vaccinations.
- Participants who received the wrong study medication.
- Participants who fulfilled exclusion criteria (e.g. participant received any nationally deployed Covid vaccine)

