##### Blinded:

- The 135 Participants in the randomised part of the study.
- Investigators and other site staff
- Biostatisticians writing the Statistical Analysis Plan and developing the statistical analysis.
- Clinical research associates (CRAs) responsible for monitoring study data.
- All laboratory personnel at central laboratories for safety and immunogenicity laboratory assessments.
- All other Sponsor and contract research organisation (CRO) staff not otherwise specified above will be unblinded as part of the Part A statistical analysis. Laboratory personnel at the Sponsor's testing labs remain blinded throughout the study for additional testing procedures.

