#### **16.5 Planned Data Analysis of the Study**

The following data analyses will be performed:

- Part A includes safety and immunogenicity data after all Participants have completed Visit 4 (Day 36).
- Part B includes safety and immunogenicity data after all Participants have completed Visit 6 (Day 208).
- An additional data analysis will be performed during part B after all Participants have completed Visit 5 (Day 106)
- Part C includes Visits 7 to 10. An analysis of Part C will be done when all participants have completed visit 9.
- Final analysis will be done when all participants have completed the last visit (visit 10)

Individual study parts will be analysed sequentially.

Part A analysis will be performed once the last Participant has completed Day 36 (Visit 4) and will comprise the primary immunogenicity and safety endpoints; the study will be unblinded at this time. Part B analysis will be performed once the last Participant has completed Day 208 (Visit 6).

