In addition to the functional assays, samples are analysed for IgG against SARS-CoV-2 by a human anti-SARS-CoV-2 pre-spike IgG antibody ELISA (S-ELISA). In brief, the SARS-CoV-2 pre-spike recombinant antigen is adsorbed onto the 96-well microplate. Dilution series of human sera, standard and controls are added to microtitre plates coated with the SARS-CoV-2 pre-spike recombinant antigen. Presence of binding IgGs is detected with an anti-human IgG antibody conjugated to peroxidase, followed by addition of the peroxidase substrate. The optical density of the colored end product is proportional to the amount anti-SARS-CoV-2 pre-spike IgG antibodies present in the serum sample. Values below the quantitation limit of the ELISA (50.3 ELU/mL) and samples scored

as “negative” will be replaced by 25 ELU/mL. Also values above the quantitation limit (>15798 ELU/mL) will be replaced by 15798 ELU/mL.

Immunogenicity analysis will be presented for the respective PPAS and modified PPAS population. In addition analysis can also be presented for FAS population. Immunogenicity analysis may also be presented for “Unscheduled COVID-19 illness visit” that will be performed if a participant tests positive for COVID-19 during the study.

Immunogenicity analysis may also be presented stratified for MNA positive/negative at Visit 1. MNA result will be considered positive if result (ND50) \geq LLOQ, i.e. ≥ 62 . Otherwise if the result (ND50) $<$ LLOQ then MNA will be considered negative.

All secondary immunogenicity analysis for booster phase will be presented by primary treatment group (Low Dose/ Medium Dose/ High Dose) of participant and the tables will also be presented stratified by following factors: Received other COVID-19 vaccine any time during study / Not received other COVID-19 vaccine any time during study/ COVID-19 positive any time during study who did not receive other COVID-19 vaccine any time during study.

Immunogenicity analysis will also be presented for participants in PPAS and mPPAS who received a booster dose.

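### The promise to classify deviations before unblinding can hold only for the Day 36 per-protocol set; membership at Day 106 and Day 208 stays open to case-by-case decisions after the Part A unblinding

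*SAP*

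**What the plan says.** **Timing.** SAP 4.5 gives one rule for every data cut: "All deviations will be evaluated and classified as major or minor before database lock and unblinding". It refers to a protocol deviation management plan for detail. Protocol 16.5 places the primary endpoints in the Part A analysis and adds that "the study will be unblinded at this time". Protocol 16.4 mentions a blind data review meeting for Part A only.

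**Membership.** SAP 4.3 builds the PPAS from participants without major deviations "until the respective analysis time point (i.e. PPAS Day 36, PPAS Day 106 and PPAS Day 208"), so there are three sets, and SAP 4.4 derives a modified set from each. It also says that "final decisions on all protocol violations will be made on a case by case decision in a data review meeting". The list of major deviations in SAP 4.5 is expressly not exhaustive. Protocol 16.2 contains the same case-by-case clause.

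**Who is blinded.** The list in Protocol 10.5 names investigators, site staff, monitors, central laboratory staff and the analysis biostatisticians as blinded, with no end date. It continues: "All other Sponsor and contract research organisation (CRO) staff not otherwise specified above will be unblinded as part of the Part A statistical analysis". Only for one group does it promise blinding to the end: "Laboratory personnel at the Sponsor's testing labs remain blinded throughout the study for additional testing procedures".

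**Analysis sets.** SAP 4.3 makes the PPAS the main set for immunogenicity. Protocol 16.4.3.2 leaves FAS immunogenicity analyses to the SAP, and SAP 8 says only: "In addition analysis can also be presented for FAS population".

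**The concern.** A per-protocol set protects a comparison only if exclusions cannot be influenced by knowledge of group and outcome. SAP 4.5 offers that protection in general terms, and a reader will take it to cover Day 106 and Day 208. For those sets it cannot apply. The Part A results by dose had already been used to select the high dose (Protocol 8.5).

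The comparisons at stake are those of antibody persistence between doses up to six months after the second vaccination, which serve the second secondary objective. Discretionary exclusions made with knowledge of dose and Day 36 response could shift them. A summary on a set without such exclusions would show whether they matter, and none is indexed.

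**Working it through.** **1. Order of events**

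| Step | Source | Timing |
|---|---|---|
| Part A last subject out | Protocol synopsis | Feb 2021 |
| Study unblinded | Protocol 16.5 | at the Part A analysis |
| High dose selected on Day 36 results | Protocol 8.5 | before protocol Version 7.0 |
| Part B (Day 208) last subject out | Protocol synopsis | planned Aug 2021 |
| Protocol version underlying this SAP | SAP 1 | 31 Aug 2021 |

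PPAS Day 106 and Day 208 depend on deviations up to those days, and some of those deviations arise after the Part A unblinding. For them, classification before unblinding is impossible. Classification before each later database lock is still possible. SAP 10 puts the Day 106 interim before the one after Visit 9, and the SAP 13.2 index first reports the Day 208 adverse-event summaries at the latter. Day 106 results by dose are therefore also likely to be known when PPAS Day 208 is settled.

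**2. Fixed and discretionary exclusions**

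- Fixed: fewer than two vaccinations and a licensed COVID-19 vaccine outside the study (SAP 4.3); a positive COVID-19 test, for the mPPAS (SAP 4.4).
- Named as examples: wrong study medication and fulfilled exclusion criteria (SAP 4.5; listed as criteria in Protocol 16.2).
- Discretionary: anything else judged major.

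**3. Index check (SAP 13.2 to 13.4)**

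- Populations in the table index: All Participants, Safety, Safety (Booster), Per-Protocol, Modified Per-Protocol (some with convalescent participants) and ITT (Booster).
- Populations in the figure index: Safety, Per-Protocol, Modified Per-Protocol and All Convalescent Participants.
- FAS tables: 0. FAS figures: 0.
- The mPPAS is a subset of the PPAS and inherits its exclusions. The ITT (Booster) tables cover Part C only.

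**4. The plan's own figure**

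SAP 2.5 assumes 10% with protocol deviations: 50 × (1 − 0.10) = 45 evaluable per group. This reproduces, so the plan expects about 5 exclusions per group, objective ones included.

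**5. Worst-case size**

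The documents give no SD for log10 titre. I assume normal log10 titres, SD 0.3 to 0.6, and 48 per arm. Dropping the k lowest values raises the mean log10 titre by SD × S/(48 − k), where S is the sum of the absolute expected values of the k lowest standard normal order statistics.

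For k = 3 the expected values are −2.233, −1.837 and −1.609, so S = 5.679 and S/45 = 0.1262.

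- SD 0.3: 10^(0.3 × 0.1262) = 1.09
- SD 0.4: 10^(0.4 × 0.1262) = 1.12
- SD 0.6: 10^(0.6 × 0.1262) = 1.19

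For k = 1 and k = 2 at SD 0.4 the ratios are 1.045 and 1.085.

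**6. Against sampling error (SD 0.4, 48 per arm)**

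- 95% CI factor for one GMT: 10^(2.012 × 0.4/√48) = 1.31
- 95% CI factor for a GMT ratio: 10^(1.986 × 0.4 × √(2/48)) = 1.45

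**The case against.** **Who decides is not stated.** It is tempting to infer that the later sets are decided by people who know dose and titre. The documents do not establish this. Protocol 10.5 lists several roles as blinded without an end date, and the attendees of the review meeting are not named. Nor is it stated that titres at the time point under analysis are available when membership is decided. This stands. What remains is that nothing in the protocol or SAP prevents it, and Protocol 10.5 and 16.5 do not agree on who is still blind after Part A.

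**The deviation management plan may cover it.** SAP 4.5 refers to that plan, which is not available here. It may set rules for later cuts. Even so, the SAP sentence is wrong as a statement about Day 106 and Day 208.

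**Exclusions are traceable.** A reader might also infer that nothing would reveal a biased exclusion. That goes too far. Listing 16.1.2.2 gives deviations at the second and third interims, Listings 16.4.1.1 and 16.4.1.2 give neutralizing titres and fold increases for all participants, and the disposition summary counts each population. An audit is possible; a summary estimate is what is missing.

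**A plain FAS is a poor check.** It keeps one-dose participants and recipients of outside vaccines, whose effect could swamp any discretionary exclusion. This is right, and the fix allows for it.

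**The stakes are modest.** SAP 2.2 states no formal hypotheses, the affected time points are secondary, and at SD 0.4 the worst-case 12% shift lies well inside a CI factor of 1.45 for a ratio. This limits the importance of the point but does not repair the text.

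**Conclusion.** The point holds as a defect in a stated safeguard, and it should be corrected. Classification before unblinding is achievable for PPAS Day 36 only. For PPAS Day 106, PPAS Day 208 and the matching mPPAS sets, the SAP leaves room for case-by-case exclusions after the unblinding of sponsor and CRO staff not otherwise specified, and it indexes no summary on a set without them.

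There is no evidence that any exclusion was biased. The likely effect is small because the main exclusions are objective. The 9% to 19% figure is a ceiling: it assumes that the three lowest responders are removed from one arm and none from the others, and it rests on an SD range and an arm size that the documents do not give.

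A reader might extend the concern to the Day 36 primary endpoint. The documents do not support that if the Part A review was blind as planned; the 15 sentinel participants were open-label by design in any case.

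**What to change.** 1. **Timing and access.** State in SAP 4.5 that classification before unblinding applies to PPAS Day 36 only. For Day 106 and Day 208, have deviations classified before each database lock by people without access to dose or immunogenicity results. Identify wrong-dose cases separately from the dispensing and IXRS records, since that check needs treatment information. Reconcile Protocol 10.5 with 16.5 on who remains blinded after Part A. If PPAS Day 106 is already fixed, record when and by whom.
2. **Criteria.** For the later sets, use the objective criteria already named: fewer than two vaccinations, wrong study medication, fulfilled exclusion criteria, and a licensed COVID-19 vaccine before the sample. Report any further case-by-case exclusion with its reason. Keep this consistent with Protocol 16.2, which carries the same clause.
3. **Supportive analysis.** Index FAS versions of Tables 14.3.1.1 and 14.3.3.1, plus a version omitting samples taken after a licensed COVID-19 vaccine, so that the comparison with the PPAS bears on discretionary exclusions rather than outside vaccination. Give counts of excluded participants by reason alongside, because one-dose and wrong-medication cases will still differ between the sets.

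Cost: SAP wording, a consistency check against the protocol, and a few extra tables from existing programs. No new data are needed.

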4.6 SAFETY ANALYSIS SET (SAS): BOOSTER GROUP

The Safety Analysis Set (SAS) for the booster phase will include all participants who received the booster vaccination. All analyses based on the SAS will be carried out using the actual treatment received.

4.7 ITT ANALYSIS SET: BOOSTER GROUP

The ITT for the booster group will include participants who received the booster dose with VLA2001.

5 GENERAL ASPECTS FOR STATISTICAL ANALYSES

5.1 GENERAL METHODS

- All analyses and summaries will be produced using SAS[®] version 9.4 (or higher).
- Categorical variables will be summarized using the number of observations (n), frequency and percentage of participants. All percentages will be presented as one-decimal point, unless otherwise specified. Percentages equal to 100 will be presented as 100% and percentages will not be presented for zero frequencies.
- Continuous variables will be summarized using the number of participants with evaluable data, mean, standard deviation (SD), median, minimum and maximum. Geometric means and corresponding statistics will be presented for titre data. The same number of decimal places as in the raw data will be presented when reporting minimum and maximum, 1 more decimal place than in the raw data will be presented when reporting the mean and median, and 2 more decimal places than in the raw data will be presented when reporting the SD. Lower and upper bound values for the confidence interval will be reported to 2 more decimal places than the raw data.
- Any calculated p-values will be presented to 3 decimal places; p-values less than 0.001 will be presented as 'p<0.001' and p-values greater than 0.999 will be presented as 'p>0.999'.
- Unscheduled or repeat assessments will not be included in summary tables unless specified. All assessments will be included in the participant listings.
- All tables, listings and figures will include footers that identify the name of the program that created the output, together with the date and time on which it was created. Headers will include the total number of pages that the presentation contains and, for each page, the number of the page within the presentation.

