### **13.4.1 Unscheduled Visit**

An unscheduled visit can be held at any time during the study if deemed necessary by the Investigator (e.g. follow-up on unexpected AEs or SAEs) or the DSMB. Assessments performed at an unscheduled visit will be at the Investigator's or DSMB's discretion. Unscheduled visits and any procedures/assessments performed during such a visit (e.g. physical examination, laboratory test) should be documented in the source data and the eCRF.

In any case a phone call will only take place if a) data are not being entered; b) grade 3 events are reported, c) if a serious AE is reported via the diary, d) if Participants indicate symptoms towards potential COVID-19 infection.

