Baseline serology will be drawn for detection of antibodies against SARS-CoV-2, HIV, HBV and HCV at the local lab. The results of SARS-CoV-2 tests that were performed up to 7 days before Visit 0 are acceptable. The results of negative HIV tests that were performed up to 30 days before Visit 0 are acceptable. A positive HIV test obtained by ELISA will have to be confirmed by a second method (e.g. Western blot or PCR) [blood (for all tests): 5 mL]. In addition, an HLA typing test will be done at Screening (20 mL)

Laboratory values will be evaluated according to the Toxicity Grading Scale for Healthy Adult and Adolescent Volunteers Enrolled in Preventive Vaccine Clinical Trials (FDA). For the individual toxicity criteria refer to section 22.4.

Laboratory assessments for which no severity grading is described in section 22.4 are graded as described in Section 15.2.1.1 upon the Investigator's judgement.

The Investigator's assessment of each abnormal laboratory value, including its clinical significance, is to be recorded in the eCRF:

- Abnormal laboratory assessments that are considered clinically relevant, in the opinion of the Investigator, need to be documented as unsolicited AEs and assessed further for severity according to the toxicity grading scale provided in Section 22.4, causality and other assessments done for unsolicited AE (see Section 15.2.1).
- Abnormal laboratory assessments that are considered a symptom of an underlying AE or part of a syndrome that is reported as AE (e.g. presence of blood cells in urine in a person diagnosed with urinary tract infection) do NOT additionally need to be documented as unsolicited AE, but a respective comment should be added to the underlying AE.

Additional tests and other evaluations required to establish the significance or aetiology of an abnormal laboratory result or to monitor the course of an AE should be obtained when clinically indicated. Any abnormal value that persists should be followed at the discretion of the Investigator.

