i An **immunogenicity sample** will be drawn [10mL] for SARS-CoV-2-specific neutralizing antibody titre evaluation and ELISA testing, development or performance of further assays related to development of this vaccine candidate and/or retrospective safety analysis if deemed necessary by the Data Safety Monitoring Board upon clinical indication or on demand if requested later by regulatory authorities.

j A blood sample [approx. 50mL] will be collected to isolate PBMCs from all Participants except sentinel Participants for future investigation of cellular immune responses to VLA2001. PBMCs may also be used for further research activities considered relevant to SARS-CoV-2, e.g., HLA typing.

k Saliva samples will be obtained from all Participants for future investigation of mucosal immune responses to VLA2001.

l All procedures/assessments (apart from e-Diary explanation and AE assessment) occur prior to vaccination (unless stated otherwise).

m A safety lab sample will be obtained if early termination occurs before Day 36 (Visit 4).

n A blood sample [approx. 50mL] will be collected to isolate serum from all Participants consenting to the additional blood volume for studies to support the establishment of a robust clinical endpoint for identification of neutralizing antibody levels associated with protection from COVID-19.

*Please note:*

- *Due to local requirements, medical history should be checked with Participants' medical records (GP / hospital) prior Day 1*

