5.3.2 Visit Windowing

Data will be analyzed using the nominal visit i.e. study visit and analysis visit will be similar. Unscheduled visits will be listed, but not mapped to a specific analysis visit.

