7.3 CLINICAL LABORATORY TESTS

Blood and urine samples will be obtained for assessment of clinical laboratory parameters. Clinical laboratory assessments (hematology, chemistry, urinalysis, coagulation) will be performed on the visits as described in the schedule of study assessments and procedures in protocol section 22.2.

Clinical laboratory parameters at all scheduled visits and the change from baseline to post baseline visits will be summarized using appropriate summary statistics by dose groups. Categorical urinalysis parameters will be summarized using count and percentages by dose cohorts for each scheduled visit.

Separate summary tables for each dose cohort and overall will be presented for the laboratory results that are marked as abnormal clinically significant by the investigator.

All clinical laboratory results will also be listed. Laboratory values that are outside the normal range will be flagged in a participant data listing.

Separate summary table and listing will be presented for the booster phase.

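### As written, SAP 5.1 and 7.3 leave results from unscheduled, repeat and COVID-19 illness visits out of the clinically significant laboratory tables

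*SAP*

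**What the plan says.** The general rule is in SAP 5.1: "Unscheduled or repeat assessments will not be included in summary tables unless specified". The next sentence there keeps every assessment in the listings. SAP 5.3.2 adds: "Unscheduled visits will be listed, but not mapped to a specific analysis visit".

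SAP 7.3 then plans two kinds of laboratory table. The descriptive tables are tied to visits: "Clinical laboratory parameters at all scheduled visits and the change from baseline to post baseline visits will be summarized". The second kind, by dose cohort and overall, is "presented for the laboratory results that are marked as abnormal clinically significant by the investigator". Nothing is said about which visits feed this second kind. In the SAP 13.2 index these are Tables 14.2.2.2, .4, .6 and .9. Their booster counterparts are .11, .13, .15 and .18, for which SAP 7.3 says only that a separate table and listing will be produced.

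Protocol 16.4.3.1 commits to reporting, per study arm and by parameter, how many participants have abnormal laboratory parameters. It sets no limit on visits. Protocol 16.4 requires any change to the planned analyses to be described and justified in the SAP. SAP 13.1 declares one change, the dropped stratification by serostatus.

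**The concern.** Restricting by-visit and change-from-baseline tables to scheduled visits is ordinary practice. A table of clinically significant abnormalities has a different purpose: it should show who had one, whenever it was found. Protocol 13.4.1 provides unscheduled visits for following up unexpected AEs and SAEs and names laboratory tests among the things that may be done there. Both assessment schedules also mark safety laboratory tests at the unplanned COVID-19 illness visit. Leaving those visits out by default removes results obtained because something was already suspected, and the omission can only lower the reported rate.

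At stake is whether the dedicated laboratory tables of a first-in-human dose-finding trial can be taken at face value. COVID-19 manifestations and complications are monitored as AESIs because of the theoretical concern about enhanced disease (protocol 15.10), so laboratory findings at illness visits are of direct interest.

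**Working it through.** There is no planned figure to reproduce. The check follows a clinically significant result from the visit where it arises to the outputs that could show it.

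**1. Where safety laboratory samples arise.** Protocol 22.2 marks them at screening, Days 8, 22, 36 and 208, the unplanned COVID-19 illness visit and early termination; footnote m limits the last to terminations before Day 36. Protocol 22.3 marks them at Visits 6 to 9, the illness visit and early termination. Protocol 13.4.1 allows them at any unscheduled visit.

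**2. Which of these SAP 5.1 removes.** Unscheduled and repeat assessments are removed directly. The illness visit is unplanned in the protocol schedules, and SAP 8 itself calls it unscheduled, so it falls under the same rule. SAP 5.3.2 closes the other route, because unscheduled visits are not mapped to an analysis visit.

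**3. Whether an exception is specified.** SAP 7.3 contains none. SAP 8 does write one for immunogenicity, saying that analysis may be presented for the illness visit. Exceptions are therefore stated where wanted, and silence in 7.3 leaves the 5.1 default in force.

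**4. What other outputs recover.** Protocol 15.7 makes a clinically relevant laboratory abnormality an unsolicited AE. Protocol 15.2.1 collects AEs at unscheduled visits whatever their source. The schedules mark AE assessment at the illness and early-termination visits. Footnote e of protocol 22.4 makes a Grade 4 laboratory value an SAE. SAP 7.2.1 tabulates unsolicited and serious AEs by dose group, with separate booster-phase summaries. Protocol 15.7 also says that abnormalities belonging to an AE already reported "do NOT additionally need to be documented as unsolicited AE"; a comment is added to that AE instead.

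| Significant result from | Dedicated laboratory table | AE or SAE table | Listing |
|---|---|---|---|
| Scheduled visit | Yes | Yes, under protocol 15.7 | Yes |
| Unscheduled, repeat or illness visit, recorded as its own AE | No | Yes | Yes |
| The same visits, below Grade 4, part of an AE already reported | No | Only under the diagnosis | Yes |
| Early termination | Unclear | As in the two rows above | Yes |

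The third row is the real gap: no summary table shows the laboratory finding as such.

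**5. Early termination.** Protocol Table 3 gives the time of this visit as unscheduled, which would bring it under SAP 5.1. SAP 5.3.1 says that all data up to discontinuation are used in the summaries and analyses. The two point in opposite directions.

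**6. Size per missed participant.** This is an illustration, not an estimate. It concerns a participant whose only significant value for a parameter came from an excluded visit.

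- Dose group of 50: 1/50 = 2.0% becomes 0/50 = 0%. The exact 95% intervals are 0.05% to 10.65% and 0% to 7.11%.
- Overall column of 150: 1/150 = 0.7%.
- Booster phase, if about 80 take part: 1/80 = 1.25%.

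The intervals are for scale only. SAP 7.3 plans none for laboratory tables.

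**The case against.** The strongest reply is that the safety information is already tabulated. A reader might infer from SAP 5.1 that significant abnormalities found at these visits appear in no by-dose safety table. The documents do not support that. The 5.1 rule concerns assessments and leaves AE records alone. Protocol 16.4.3.1 expressly includes clinically relevant laboratory changes among the unsolicited AEs presented by arm. Even for an abnormality folded into a diagnosis, the diagnosis itself is tabulated. This part of the reply stands and limits the point to the dedicated laboratory tables.

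A reader might also infer that the early-termination sample is never tabulated. That is too strong. SAP 5.3.1 points the other way, early termination has its own column in the schedules, and the word in Table 3 may mean only that the visit has no fixed date. What remains is an ambiguity to settle.

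Third, SAP 7.3 puts no visit limit on the clinically significant tables, SAP 5.1 allows specified exceptions, and the table specifications are written after the SAP (SAP 12.1). A programmer might therefore include every result. That is possible, but it would go against the stated default, and the choice would rest outside the SAP.

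Finally, every result is listed and out-of-range values are flagged. That is true, but a listing does not provide the per-arm count that protocol 16.4.3.1 promises.

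**Conclusion.** The point holds as an undercount in the dedicated clinically significant laboratory tables. It affects unscheduled, repeat and COVID-19 illness visits, is narrower than protocol 16.4.3.1, and is not declared in SAP 13.1. It matters most for abnormalities treated as part of an AE already reported, which is likely at illness visits.

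The number of participants affected cannot be derived from the documents. A reader might try to size it from the long interval between the scheduled samples on Day 36 and Day 208. That interval measures calendar time, not results lost, and says nothing about how many samples are taken in it.

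The conclusion assumes that SAP 5.1 is applied literally, that no later table specification overrides it, and that the protocol's clinically relevant and the SAP's clinically significant denote the same investigator judgement. If the last assumption fails, fewer of these results may reach the AE tables. The point is worth correcting because the remedy is cheap; it does not call the trial's main safety analysis into question.

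**What to change.** Add to SAP 7.3, as a specified exception to 5.1:

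> Tables of clinically significant laboratory results count each participant once per parameter, using any post-dose assessment (scheduled, unscheduled, repeat, COVID-19 illness or early-termination visit); by-visit and change-from-baseline tables use scheduled visits only.

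This also settles the early-termination question for these tables. For the booster tables, post-dose should mean after the booster, and the primary-phase tables should stop at the booster so that no result is counted in both. If the sponsor prefers scheduled visits only, that choice should be declared and justified in SAP 13.1.

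The cost is one sentence and one derivation flag, with no new data. The SAP 13.2 index marks these tables as not included in any of the three interim analyses, so according to the index no interim output would need to be redone. The downside is that reported abnormality rates may rise slightly.
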